# 12.6.2 Evaluable Disease

Evaluable disease is defined as at least one lesion, with no lesion that can be accurately measured in at least one dimension. Such lesions may be evaluable by nuclear medicine techniques, immunocytochemistry techniques, tumor markers, CSF cytology, or other reliable measures.

# 12.6.3 Selection of Target and Non-Target Lesions

For most CNS tumors, only one lesion/mass is present and therefore is considered a "target" for measurement/follow up to assess for tumor progression/response. If multiple measurable lesions are present, up to 5 should be selected as "target" lesions. Target lesions should be selected on the basis of size and suitability for accurate repeated measurements. All other lesions will be followed as non-target lesions. The lower size limit of the target lesion(s) should be at least twice the thickness of the slices showing the tumor to decrease the partial volume effect (e.g., 8 mm lesion for a 4 mm slice).

Any change in size of non-target lesions should be noted, though does not need to be measured.

# 12.6.4 Response Criteria for Target Lesions

Response criteria are assessed based on the product of the longest diameter and its longest perpendicular diameter. Development of new disease or progression in any established lesions is considered progressive disease, regardless of response in other lesions - e.g., when multiple lesions show opposite responses, the progressive disease takes precedence. Response Criteria for target lesions:

- Complete Response (CR): Disappearance of all target lesions.
- Partial response (PR): ≥ 50% decrease in the sum of the products of the two perpendicular diameters of all target lesions (up to 5), taking as reference the initial baseline measurements.
- Stable Disease (SD): Neither sufficient decrease in the sum of the products of the two perpendicular diameters of all target lesions to qualify for PR, nor sufficient increase in a single target lesion to qualify for PD.
- Progressive Disease (PD): 25% or more increase in the sum of the products of the perpendicular diameters of the target lesions, taking as reference the smallest sum of the products observed since the start of treatment, or the appearance of one or more new lesions.

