## 12.7 Best Response

## 12.7.1 Evaluation of Best Overall Response

The best overall response is the best response recorded from the start of the treatment until disease progression/recurrence (taking as reference for progressive disease the smallest measurements recorded since the treatment started). The patient's best response assignment will depend on the achievement of both measurement and confirmation criteria.

Table 3. Sequences of overall response assessments with corresponding best response.

1st Assessment	2nd Assessment	Best Response
Progression		Progressive disease
Stable, PR, CR	Progression	Progressive disease
Stable	Stable	Stable
Stable	PR, CR	Stable
Stable	Not done	Not RECIST classifiable
PR	PR	PR

PR	CR	PR
PR, CR	Not done	Not RECIST classifiable
CR	CR	CR

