**ADVL1515** 

#### 12.7.2 Duration of Response

Duration of overall response: The duration of overall response is measured from the time measurement criteria are met for CR or PR (whichever is first recorded) until the first date that recurrent or progressive disease is objectively documented (taking as reference for progressive disease the smallest measurements recorded since the treatment started).

The duration of overall CR is measured from the time measurement criteria are first met for CR until the first date that progressive disease is objectively documented.

Duration of stable disease: Stable disease is measured from the start of the treatment until the criteria for progression are met, taking as reference the smallest measurements recorded since the treatment started, including the baseline measurements.

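### For CNS tumors with two or more target lesions, Section 12.6.4 limits stable disease by growth of a single lesion, but its progression criterion tests only the sum of products

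*Combined protocol and SAP*

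**What the plan says.** Section 12.6.4 of the combined protocol and SAP defines target-lesion response for CNS tumors on products of perpendicular diameters. Four of its statements matter here.

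- **Lead-in:** "Development of new disease or progression in any established lesions is considered progressive disease, regardless of response in other lesions". Its example adds that "when multiple lesions show opposite responses, the progressive disease takes precedence". No percentage is given.
- **PR:** a fall of at least 50% in the sum of products, "taking as reference the initial baseline measurements".
- **SD:** not enough decrease in the sum for PR, "nor sufficient increase in a single target lesion to qualify for PD".
- **PD:** "25% or more increase in the sum of the products of the perpendicular diameters of the target lesions", or any new lesion. The percentage is measured from the lowest point of the sum: "taking as reference the smallest sum of the products observed since the start of treatment".

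Section 12.6.3 allows up to five target lesions but says that most CNS tumors have only one. Section 12.6.5 covers non-target lesions only. The table in Section 12.6.7 takes one target-lesion category as its input. Section 12.7.1 gives a general reference for progression, "taking as reference for progressive disease the smallest measurements recorded since the treatment started", and the stable-disease paragraph of Section 12.7.2 has "taking as reference the smallest measurements recorded since the treatment started, including the baseline measurements". Neither section gives a percentage for one lesion.

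**The concern.** The SD criterion points to a single-lesion test for PD that the PD criterion does not contain. When one lesion grows and the sum rises by less than 25%, a reader who applies the PD criterion does not call PD. A reader who applies the SD limit, or the lead-in at face value, may call it. The disagreement is PD versus SD when the other lesions are stable, and PD versus PR when they shrink enough.

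The category is used in several places. Section 5.2 requires at least stable disease to start another cycle. Section 10.1(a) makes radiographic progression a reason for removal from protocol therapy. In Table 3 of Section 12.7.1, PR followed by PR is a best response of PR, while PR followed by progression is progressive disease. Section 12.7.2 ends the duration of stable disease when the progression criteria are met. Section 12.2.4.1, for solid tumors outside the CNS, does not have this gap: its SD definition does not bring in a single lesion, and its percentage test for PD is on the sum.

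**Working it through.** The plan gives no figure of its own to reproduce. The check applies the printed thresholds (PR: sum down 50% or more from baseline; PD: sum up 25% or more from the smallest sum) to lesion sizes chosen for illustration. In each example the starting sum is taken as both the baseline and the smallest sum so far.

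**One target lesion.** The sum is that lesion's product. Going from 400 to 500 mm² is +25% on either test, so there is no conflict.

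**Two lesions, the larger one stable.** The larger is 20×20 = 400 mm². The smaller goes from 10×10 = 100 to 14×14 = 196 mm².
- Smaller lesion: 196/100 − 1 = +96%.
- Sum: (400+196)/(400+100) − 1 = 596/500 − 1 = +19.2%.
- The PD criterion is not met, although one lesion has nearly doubled in product. It is first met when the smaller lesion reaches 15×15 = 225 mm²: 625/500 − 1 = +25.0%, with that lesion at +125%.

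**Two lesions, the larger one shrinking.** The lesions go from 900 and 100 mm² to 360 and 140 mm².
- Lesions: 360/900 − 1 = −60%, and 140/100 − 1 = +40%.
- Sum: (360+140)/(900+100) − 1 = 500/1000 − 1 = −50.0%.
- The PR criterion is met. If +40% in one lesion counts as progression, the lead-in makes the scan PD.

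**General case, other lesions stable.** If one lesion holds share w of the smallest sum and grows by g, the sum grows by w × g. The PD criterion therefore needs g ≥ 25%/w. With k equal lesions, w = 1/k and g ≥ 25k%:

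| Equal target lesions (k) | Growth of one lesion before the PD criterion is met |
|---|---|
| 1 | 25% |
| 2 | 50% |
| 3 | 75% |
| 4 | 100% |
| 5 | 125% |

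The gap between the two tests widens with the number of lesions and is widest for the smallest lesion.

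**The case against.** Several points on the other side have weight.

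- **A route without a number can still be used.** A reader might infer that a single-lesion call is impossible without a percentage. The documents do not support that: Sections 12.2.4.2 and 12.6.5 both use unequivocal progression of non-target lesions with no figure. A qualitative call is possible, but it is less reproducible than a numeric one.
- **The lead-in can be read more narrowly.** It speaks of established lesions, not target lesions. It could mean only that new disease or non-target progression overrides target response, as the Section 12.6.7 table provides. Its place under the target-lesion heading and its example of lesions with opposite responses make a lesion-level reading more natural, but not certain. The firm mismatch is between the SD and PD criteria.
- **Precedence is already printed.** Once a lesion is judged progressive, the lead-in rules out PR. That leaves open how much growth makes a single lesion progressive.
- **Central review helps in part.** Section 8.2 sends CR, PR and SD of six or more cycles to central review. This may limit site-to-site variation in those categories, but it supplies no threshold and does not list PD calls.

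A reader might carry the 25% over to a single lesion, but the text ties both that figure and its reference to the sum. A reader might also infer that the conflict runs the other way, with PD by the sum and not by a single lesion. That would need a single-lesion threshold above 25%, and the documents state none.

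**Conclusion.** The concern holds as a wording conflict within Section 12.6.4, confined to CNS patients with two or more target lesions. The SD limit refers to a single-lesion test that the PD criterion lacks, and Sections 12.6 and 12.7 give no percentage for one. The same scan can therefore be PD or SD, or PD or PR. In the illustrations one lesion grows by 96% or 40% while the sum changes by +19.2% or −50%. Those sizes are assumptions, and the documents do not allow an estimate of how many patients would be affected, because they give no planned CNS count.

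Priority is low. Section 12.6.3 expects one lesion in most CNS tumors. Response is a secondary aim (Section 1.2.1) reported descriptively (Section 11.5). Section 10.1 also lists clinical progression and physician judgement as grounds for removal. A reader might infer that dose-finding is at risk; it is not, because the DLT and MTD rules do not use this category.

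**What to change.** Reconcile the lead-in, the SD criterion and the PD criterion in Section 12.6.4 so that all three name the same progression route or routes: the sum, a single lesion, or either, at the sponsor's choice. For each route, state the threshold and the reference value in Section 12.6.4 itself, including whether baseline counts, because Section 12.7 says so only in its stable-disease paragraph.

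State the order of categories in the list. PD overrides PR, as the lead-in already implies. CR takes priority over PR when all target lesions disappear, because that scan also meets the 50% decrease for PR. Then define SD as none of CR, PR or PD, so that each assessed scan falls in one category.

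The cost is wording in one section. No new measurements are needed, because the sum of products already requires both diameters of every target lesion.

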# 12.6.5 Response Criteria for Non-Target Lesions:

- Complete Response (CR): Disappearance of all non-target lesions.
- Incomplete Response/Stable Disease (IR/SD): The persistence of one or more non-target lesions.
- **Progressive Disease (PD):** The appearance of one or more new lesions and/or unequivocal progression of existing non-target lesions.

## 12.6.6 Response criteria for tumor markers (if available):

Tumor markers will be classified simply as being at normal levels or at abnormally high levels.

### 12.6.7 Overall Response Assessment

The overall response assessment takes into account response in both target and non-target lesions, the appearance of new lesions and normalization of markers (where applicable), according to the criteria described in the table below. The overall response assessment is shown in the last column, and depends on the assessments of target, non-target, marker and new lesions in the preceding columns.

Target Lesions	Non-target Lesions	Markers	New Lesions	Overall Response
CR	CR	Normal	No	CR
CR	IR/SD	Normal	No	PR
CR	CR, IR/SD	Abnormal	No	PR
PR	CR, IR/SD	Any	No	PR
SD	CR, IR/SD	Any	No	SD
PD	Any	Any	Yes or No	PD
Any	PD	Any	Yes or No	PD
Any	Any	Any	Yes	PD

Each patient will be classified according to his "best response" for the purposes of analysis of treatment effect. Best response is determined as outlined in Section 12.7 from a sequence of overall response assessments.

## 12.7 Best Response

## 12.7.1 Evaluation of Best Overall Response

The best overall response is the best response recorded from the start of the treatment until disease progression/recurrence (taking as reference for progressive disease the smallest measurements recorded since the treatment started). The patient's best response assignment will depend on the achievement of both measurement and confirmation criteria.

Table 3. Sequences of overall response assessments with corresponding best response.

1st Assessment	2nd Assessment	Best Response
Progression		Progressive disease
Stable, PR, CR	Progression	Progressive disease
Stable	Stable	Stable
Stable	PR, CR	Stable
Stable	Not done	Not RECIST classifiable
PR	PR	PR

PR	CR	PR
PR, CR	Not done	Not RECIST classifiable
CR	CR	CR

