## 12.2.5 Overall Response Assessment

Table 1:	For Patients with Measurable Disease	(i.e., Target Disease)

Target Lesions	Non-Target Lesions	New Lesions	Overall Response	Best Overall Response when Confirmation is
CD	CD	NT	CD	Required*
CR	CR	No	CR	$\geq$ 28 days Confirmation
CR	Non-	No	PR	
	CR/Non-PD			$\geq$ 28 days Confirmation
CR	Not evaluated	No	PR	
PR	Non-	No	PR	
	CR/Non-			
	PD/not			
	evaluated			
SD	Non-	No	SD	documented at least once $\geq$
	CR/Non-			28 days from baseline
	PD/not			-
	evaluated			
PD	Any	Yes or No	PD	
Any	PD**	Yes or No	PD	no prior SD, PR or CR
Any	Any	Yes	PD	
* See REC	IST 1.1 manuscript	for further deta	ails on what is	evidence of a new lesion.

\*\* In exceptional circumstances, unequivocal progression in non-target lesions may be accepted as disease progression.

Note: Patients with a global deterioration of health status requiring discontinuation of treatment without objective evidence of disease progression at that time should be reported as "*symptomatic deterioration*." Every effort should be made to document the objective progression even after discontinuation of treatment.

Table 2: For Patients with Non-Measurable Disease (i.e., Non-Target Disease)

Non-Target Lesions	New Lesions	Overall Response
CR	No	CR
Non-CR/non-PD	No	Non-CR/non-PD*
Not all evaluated	No	not evaluated
Unequivocal PD	Yes or No	PD
Any	Yes	PD

\* 'Non-CR/non-PD' is preferred over 'stable disease' for non-target disease since SD is increasingly used as an endpoint for assessment of efficacy in some trials so to assign this category when no lesions can be measured is not advised

CT/MRI	MIBG	Bone Scan	Bone Marrow	Catechol	Overall
PD	Any	Any	Any	Any	PD
Any	PD	Any	Any	Any	PD
Any	Any	PD	Any	Any	PD
Any	Any	Any	PD	Any	PD
SD	CR/PR/SD	Non-PD	Non-PD	Any	SD
PR	CR/PR	Non-PD	Non-PD	Any	PR
CR/PR	PR	Non-PD	Non-PD	Any	PR
CR	CR	Non-PD	Non-PD	Elevated	PR
CR	CR	CR	CR	Normal	CR

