#### 12.2.6 Overall Best Response Assessment

Each patient will be classified according to his "best response" for the purposes of analysis of treatment effect. Best response is determined as outlined in Section 12.7 from a sequence of overall response assessments.

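### For measurable solid tumours, Tables 1 and 3 give different best responses when stable disease is followed by progression or by no further scan

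*Combined protocol and SAP*

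**What the plan says.** Two places in the combined protocol and SAP state best-response criteria for patients with measurable solid tumours.

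- **Section 12.2.5, Table 1.** The last column is for best overall response when confirmation is required. Its SD entry asks only that SD be "documented at least once", at least 28 days from baseline. Among the rows for progressive disease (PD) the same column prints "no prior SD, PR or CR".
- **Section 12.7.1, Table 3.** One row reads "Stable, PR, CR Progression Progressive disease". Another reads "Stable Not done Not RECIST classifiable". A third reads "Stable PR, CR Stable".

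Section 12.2.6 says that best response in this group is determined as set out in Section 12.7, "from a sequence of overall response assessments". The evaluable-only, MIBG-positive, marrow and CNS groups are also sent to Section 12.7.

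Above Table 3, Section 12.7.1 gives a definition, "The best overall response is the best response recorded from the start of the treatment until disease progression/recurrence", and then a condition: "The patient's best response assignment will depend on the achievement of both measurement and confirmation criteria".

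Section 12.2 and note 5 to the schedule in Section 8.1 call for a confirmatory scan on the next consecutive cycle after a response is first documented. Neither limits this to responses seen at the first assessment.

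**The concern.** Take a patient whose first scan shows SD at least 28 days from baseline. If the next scan shows progression, Table 1 supports a best response of SD and Table 3 says PD. If there is no next scan, Table 1 still supports SD and Table 3 says the patient cannot be classified.

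Table 3 also does not say whether its two columns are the first two scans on study, or a finding and its confirmation. On the first reading, a patient with SD, then PR, then PR is Stable, and so is one with SD, CR, CR. On the second they are PR and CR.

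Best response is the classification named for analysing treatment effect, and it serves secondary aim 1.2.1. If the rule is settled only when the data are in hand, the split between SD, PD and unclassifiable becomes a choice made after seeing results.

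**Working it through.** The plan gives no figure to reproduce. The check compares the two tables and works out the scan timing.

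**1. The two tables side by side**, with any SD documented at least 28 days from baseline:

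| Sequence | Table 1, best-response column | Table 3 |
|---|---|---|
| PD first | PD | PD |
| SD, then PD | SD | PD |
| SD, then SD | SD | SD |
| SD, then PR or CR | SD (response not yet confirmed) | SD |
| SD, then not done | SD | not classifiable |
| PR, then PR | PR | PR |
| CR, then CR | CR | CR |

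The tables disagree in two rows: SD then PD, and SD then not done. Both disagreements rest on Table 1's SD entry alone.

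**2. Is Table 1's 28-day condition usually met at the first scan?** Inputs: baseline imaging 0 to 14 days before the start of therapy (Section 4.0), first evaluation at the end of Cycle 1 (Section 8.1), 28-day cycles (Section 5.1).

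- Scan on Day 28: 28 − 1 = 27 days after Day 1. Adding 0 to 14 gives 27 to 41 days after the baseline scan. The condition is met unless the baseline scan was on Day 1 itself.
- If the 72-hour window in Section 8.1 also covers imaging, the scan falls on Day 26 to 29, which gives 25 to 42 days. There are 15 × 4 = 60 whole-day combinations. Those under 28 days number 3 (Day 26) + 2 (Day 27) + 1 (Day 28) + 0 (Day 29) = 6, so 54 of 60 meet the condition.

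The conflict therefore arises under most permitted timings.

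**3. How long must SD last under Table 3?** A patient with SD at the first scan is classed as Stable only if a second scan is done and does not show progression. The schedule asks for scans every other cycle after the one at the end of Cycle 1, which can be counted in two ways.

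- Second scan at the end of Cycle 2 (Day 56): 56 − 1 = 55, plus 0 to 14 = 55 to 69 days from the baseline scan.
- Second scan at the end of Cycle 3 (Day 84): 84 − 1 = 83, plus 0 to 14 = 83 to 97 days.

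Either is longer than Table 1's 28 days.

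**4. Section 12.7.1 against Table 3.** For SD then progression, the best response recorded before progression is SD, so the first sentence favours SD. The second sentence adds confirmation. If confirmation is meant to cover SD, Table 3 follows from it. If it covers only PR and CR, Table 3 does not. The text does not say which.

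**The case against.** The strongest defence is that the protocol names its route. Section 12.2.6 sends these patients to Section 12.7, and only Table 3 classifies sequences. Table 1 sits under a heading about overall response at one assessment, so its last column could be a leftover that was never aligned. This largely stands: the analyst is pointed to Table 3. But nothing withdraws Table 1's criterion or says that Table 3 prevails over it, so the document still states two rules with different results.

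A second defence is that the two sentences of Section 12.7.1, read together, fit a rule that SD must be confirmed. That also stands as a possible reading. A reader might infer that Section 12.7.1 flatly contradicts its own table. The confirmation sentence prevents that conclusion, and in the groups outside Table 1 the matter is only an ambiguity.

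A third defence is that reading Table 3 as the first two scans only is strained, because Sections 8.1 and 12.2 require confirmation after any first documentation of response. That makes the finding-plus-confirmation reading the more natural one. The table still does not state it, and its literal row gives Stable.

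A reader might also infer from the entry in Table 1's PD rows that an unconfirmed PR or CR followed by progression conflicts with Table 3 too. Table 1 is broken in the available text, and which rows that entry covers is a guess. The point does not rely on it.

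**Conclusion.** The concern holds, as a minor one. For measurable solid tumours, two stated rules give different best responses for SD then progression and for SD then no further scan, provided the SD is at least 28 days from baseline. The undefined columns of Table 3 add a second, smaller uncertainty about responses that appear after an initial SD.

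It would be wrong to infer that the trial's main conclusions are at risk. Section 11.5 makes the response analysis descriptive and exploratory, and the MTD, the DLT rules and the sample size do not depend on it. The two conflicting sequences move patients between SD, PD and unclassifiable. They do not change the counts of confirmed CR or PR, which could change only through the literal reading of Table 3's columns. The documents give no basis for estimating how many patients would be affected.

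The day counts assume scans on the last day of the cycle and count from the baseline scan. The choice between 55 to 69 and 83 to 97 days depends on how the schedule wording is read, and the documents allow either.

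**What to change.** Before response is analysed, reconcile Table 3, Table 1's best-response column and the definition in Section 12.7.1:

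1. State one rule for SD then progression and for SD then no further scan, and apply it to every disease group sent to Section 12.7. Table 1 and the first sentence of Section 12.7.1 point to SD when it is documented at least 28 days from baseline. If a confirmed-SD rule is intended instead, say so and amend Table 1's SD entry.
2. State that a PR or CR first seen at any assessment and confirmed at least 28 days later counts as PR or CR, so that SD, PR, PR is PR and SD, CR, CR is CR.

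The cost is the wording of the two tables and one definition. No new scans or data are needed.
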